## 6. Risk/Benefit Assessment

### A. Risks

The risk to participants in this research is minimal when applying NIMH risk standards and designations. According to these NIMH guidelines, *“minimal risk to subjects means that the probability and magnitude of harm or discomfort anticipated in the research are not greater than those ordinarily encountered in daily life or during the performance of routine physical and psychological examinations or tests and that confidentiality is adequately protected. This category includes protocols that pose “no greater than minimal risk” according to federal regulations.”*

This study includes patients and health care provider participants. Not all potential study risks listed here will be relevant for all participants.

This study seeks to include patients currently acutely suicidal and/or recently hospitalized because of suicidality. By definition, these patients are inherently high-risk participants; however, the question to consider for this research is whether the study procedures, including the clinical intervention, is likely to make the participants more suicidal. We believe the answer is no. Some patient participants may feel distressed while completing study procedures and survey measures because of the content, which includes questions about suicidality, use of acute crisis tolerance skills, and coping with acute distress. Some patient participants may find these questions distressing as they could remind them of the reason for their hospitalization. On the other hand, the assessments could potentially be helpful to the patient participants as they reflect over their recent experiences and view the bigger picture of their treatment. Even with this sensitive population, we believe the risk to be low, particularly because the Site Contact or a designee or outpatient provider will determine who is sufficiently stable to engage in the research and will rule out those who are considered to be at considerable psychotic and/or so agitated that engagement in the study could cause harm. Nevertheless, this concern will be first and foremost in our minds as we implement the study procedures, and in our discussions with our suicide expert advisors and DSMB members.

Physical, social, economic, or legal risks from participating for patients and providers are expected to be low to non-existent. However, it is conceivable that a data breach could lead to work/insurance discrimination based on a patient's history of suicidal behavior.

Other potential study risks include:

- discomfort sharing personal experiences and opinions
- discomfort providing negative feedback on the tool or responding to questionnaires
- feeling pressure to participate because they are being referred to the study by their treatment provider (in the case of patients) or their supervisor (in the case of professional participants)
- impact on treatment
- data charges
- There is also the potential risk of loss of confidentiality

There are no known alternative procedures to assess this information. The primary alternative to participating in the

research is to elect not to participate in the research, which participants may do at any time without change to any current or future medical care, benefits, or employment.

## **B. Prevention of Risks**

The primary focus of this summative evaluation will be to gather qualitative and quantitative data regarding the patient participant's suicidality, use of coping skills and acute crisis tolerance skills, ED or outpatient experience, and feedback about the app (in the case of patients in the Jaspr [ED study] or JAH [Telehealth study] conditions). To address potential discomfort in sharing personal experiences, opinions, and criticism about the app and/or negative experiences during the follow up interviews and surveys, the interviewer will assure the participant that any and all feedback is helpful and that they may choose how much or little they wish to share. For the ED study, the baseline assessment with patient participants will occur in the ED in where medical and clinical staff are available to provide assistance in the unlikely event that the patient becomes upset during the study procedures. During in-person testing, the study assessment will take place in a quiet, private room provided by the hospital or in the patient's private ED room. All follow up assessments (and baseline assessment for the Telehealth study) will be conducted remotely via phone and internet, and the participant will be advised to schedule the call at a time when they can be in a private, quiet area.

Other potential risks for patient participants assigned to the Jaspr condition include the provider's overreliance on Jaspr, superseding their own independent analysis and/or an incomplete or faulty imminent distress brief intervention, which could ultimately cause harm. Providers will be encouraged to use their own clinical judgment when deciding how/when to incorporate Jaspr and the reports it provides. Regarding the patient's use of Jaspr-at-Home, the app is meant to be used only after discharge and research staff and/or Boys Town crisis counselors are available to support patients in any way they need.

All participants will be provided with complete disclosure regarding what explicitly will be asked of them using an Informed Consent procedure. The Informed Consent form will describe the procedures of the study and clarify that the study is completely voluntary and that they may decline to participate at any time. Although potential participants may be informed of the study by their supervisors (in the case of providers), or their providers (in the case of patients), it will be made clear to all potential participants that the study is completely voluntary and will not affect their standing with their agency, provider, or treatment (i.e., that they will receive treatment regardless of their participation) in any way. Organizations and providers will be informed that there should be no coercion of potential participants to take part in the research. In addition, we will provide partnering organizations with detailed instructions and scripts on how to provide information about this study to potential participants.

Should adverse events occur during the study, we will thoroughly assess factors that contributed to the adverse event, including use of Jaspr or JAH, and will seek resolution of those problems related to the study. We will notify the IRB and our DSMB of adverse events, seek their recommendations, modify the protocol, and seek IRB approval for the modification.

[name] will collaborate closely with the IRB and DSMB throughout the study to ensure proper management of high-risk situations. [name] will be consulted for concurrence with the plan on imminent-risk situations as well. If the participant becomes distressed during the baseline session, the study staff initiates a warm hand off to a provider on the spot so that the patient may receive assistance in mood improvement or safety planning from their clinical team or other trained professional. During follow up assessments, if the participant sounds distressed or indicates suicidality or self-harm intentions, the researcher conducting the follow up interview will initiate a warm hand off at the end of the interview to a Boys Town counselor to conduct risk assessment and provide resources as necessary. Boys Town will provide study staff with call documentation by the next business day and the study PI will determine actions to take; if

the DSMB and/or IRB need to be informed.

Steps will be taken to ensure that participation is voluntary and that participants' privacy and the data collected from the participants are protected.

#### *Protection from Feeling Discomfort*

The primary focus of the summative studies is to evaluate Jaspr and JAH, respectively. To address potential discomfort in sharing criticism during the study session, the interviewer will assure the participant that any and all feedback is helpful and the main reason for conducting the study.

#### *Protection from Coercion*

Participants will be told that their participation is completely voluntary, and that they may change their minds and withdraw at any time. Participants will be told that their choice to participate or not will in no way affect their relationship with their treatment providers, the usual care they are eligible to receive, and/or their colleagues.

#### *Protection from Potential Delayed Treatment*

The participants' medical care is the most important thing. Study procedures will be paused if a member of the care team needs to talk with or proceed with other medical care with the patient participant, and resume when the patient is available again.

#### *Protection from Potential Data Charge*

This is applicable only to participants in the Jaspr and JAH conditions. Participants will be told that they may choose to use the app at any time and they may choose to use it only when on Wi-Fi connection. They may also log out of the app and only log back in when they are comfortable doing so. We will also recommend checking with their smartphone data provider to ensure they know how much data they may use each billing period without incurring extra charges.

#### *Protection from Loss of Confidentiality*

Data will be protected and stored as described above in Protection of Study Data. In addition, we will destroy all files that have any names or other identifying information five years after the study is finished, including the file that links participant names to study IDs.

### **C. Adverse Events**

For this study, we define an adverse event as any untoward or unfavorable occurrence, including significant increases in distress during the study interview, or symptom associated with the participant's participation in the research, *whether or not considered related to their participation in the research*. Serious adverse events include suicide attempt, non-suicidal self-injury, significant increase in suicidal ideation, and/or significant increase in agitation while participating in the study, as reported by the participant, or observed and/or reported by their healthcare provider, and/or a member of the research team. Given the minimal risk nature of this study, likely causes of such adverse events may include one or more of the following factors: frustration with the extensive length of stay in the ED (frequently considerably longer than the usual length of stay for patients with a medical crisis); nicotine withdraw caused from long lengths of stay in patients addicted to nicotine; and dissatisfaction with the care they are receiving while in the ED or with the discharge disposition provided by their physician.

Should adverse events occur during the study, we will thoroughly assess factors that contributed to the adverse event, including use of Jaspr or JAH, and will seek resolution of those problems related to the study. Regardless of the cause of the adverse event, we will notify the IRB and our DSMB of adverse events within 10 business days, should they occur, and seek their recommendations. Fatal or life-threatening events, should they occur, will be reported to the IRB.

immediately.

All participants will be provided with information about how to report Potential Adverse Events. In addition, patient participants will be encouraged to report any Potential Adverse Events directly to the provider who is in charge of their care. Potential Adverse Event reports will be monitored daily by study staff. Because the risks to participation are low, the likelihood of Adverse Events related to the proposed research is judged to be low. In the event that a Potential Adverse Event is reported, the PI will be notified immediately. The PI will then assess the situation and determine an appropriate clinical and ethical course of action, including report of an Adverse Event to the IRB and DSMB.

[name] will work closely with the research staff to maintain continuous, close monitoring and promptly report adverse events. The study coordinators will notify [name] of any adverse events within 24 hours of occurring and notification will be forwarded to the DSMB and IRB within ten business days; fatal or life-threatening events will be reported to [name] immediately and she will notify the IRB and DSMB right away.

#### **D. Benefits**

There are no direct benefits from participating in this study; however, there are several indirect benefits for participation. Some participants may feel personal reward by engaging in testing to help further develop and polish the Jaspr tool designed to support medical personnel and suicidal patients in ED settings. Findings from this study will be used to develop a product that is intended to increase quality of care for patients who recently made a suicide attempt or are struggling with suicidal ideation. Participants directly interacting with Jaspr may benefit from perceived improved care as a result of their direct interaction and their provider's interaction with the tools. Provider participants may benefit from using Jaspr while providing risk assessments and management while also learning CAMS. Providers may also experience less distress when assessing, treating, and deciding disposition for their suicidal patients. We believe the potential benefits to science and standard of care for suicidal patients outweigh the risks associated with participation in this research.

The proposed research contributes to the goal of improving quality of care for suicidal patients, particularly in EDs where there is often a lack of sufficient time and mental health resources. Developing a successful and efficient relational agent based on the CAMS approach means that suicidal patients will receive evidence-based assessment and treatment delivered in a more timely, effective, and efficient manner than is typical in EDs and other settings.

## **7. Participant Recruitment and Informed Consent**

#### **A. Recruiting**

Suicidal patients and their providers will be recruited from hospitals/organizations nationwide. Interested providers from each site will be recruited and enrolled on a first-come, first-served basis. Patient participants will similarly be recruited on a first-come, first-served basis.

**ED Study:** Each designated project site that has agreed to participate will designate a person within the ED to serve as our “site contact” when conducting research with patient participants. We will specifically coordinate who the onsite contact would like to initially approach as potential participants and proceed as they prefer at each site. Because our access is linked to the onsite contact’s authority and oversight of the ED, our intention is to ensure we proceed in a way that is consistent with their preferred approach. In the case where the site contact or their designee prefers to inform sufficiently stable (according to usual hospital procedures and using their own clinical judgment) suicidal patients about

the study and ask if they are interested in talking to the researchers about the project. The purpose will only be to briefly mention that they may qualify for a research study taking place at their site for patients who are in the ED because of suicidal behaviors and to ask the patient if they would be interested in speaking with a member of the research team to find out more. While not required, site contacts or their designee may choose to also mention that: a) the study is completely voluntary; they do not need to participate; b) their decision – whatever it is – will in no way affect relationship with their treatment team and that they will receive care regardless; and c) study involvement that day may include using an app as part of their care or receiving the care the provider/hospital normally provides, completing a brief interview, and completing survey measures online today and at three time points over the next 90 days. While all these components will be repeated as part of the Informed Consent process by the researchers, we anticipate that some onsite contacts may prefer to briefly mention the study to their patients personally before a stranger enters the room or have a member of the care team do so on their behalf.

**Telehealth Study:** Outpatient individuals experiencing suicidality will learn of the study from their outpatient provider. Interested individuals will contact the researchers via email or phone to determine eligibility and subsequently the informed consent process if eligible.

While all informed consent procedures will be fully and thoroughly conducted by the researchers (e.g., orienting prospective participants to the study details, highlighting that they are under no obligation to participate in the study, and that a decision to decline participation will not affect the fact that they will receive treatment; the research will be paused whenever necessary so as not to interfere with the patient's medical treatment), the onsite contact may *informally* mention that the study is optional and that it will not impact their care in any way. Onsite contacts will be knowledgeable about the study's inclusion/exclusion criteria only to the degree that they can help identify which patients to speak with about the study. They will not be expected to formally screen the patient for study eligibility; this will instead be performed by a researcher prior to commencing with the informed consent procedures.

In the event that the site contact prefers to have the researchers initially approach a prospective patient, the onsite contact will then inform the researchers how to determine which patients we are permitted to approach based on study inclusion/exclusion criteria and/or other ED or outpatient policies and procedures. For example, it may involve looking at the status on a patient whiteboard and/or asking the charge nurse if the suicidal patient is sufficiently stable to talk about the study.

**ED Study only:** Once a prospective patient participant is identified, before proceeding further, if the patient isn't already in a private room, the researchers will proceed with the patient to a private area designated by the site contact. The researchers will enter the private room with the patient, introduce him/herself, and request permission to describe briefly the study using the following script or a close proximity that allows for natural conversation with the patient: *"Hello. My name is <name>. I am a researcher here at <site name>. I know you're going through a lot right now but I'm wondering if it would be okay to talk to you about a research study we have going on right now and see if you might want to take part in it? If not, that's absolutely fine."* (Intention is to get verbal permission to proceed). If patient indicates a preference to not speak with the researchers, then the researchers will simply say: *"That is of course totally fine. Should you change your mind while you're here, just let the staff know and I'll come back."* If the patient indicates interest in learning more about the study, then the researchers will thank the patient and proceed to eligibility screening and (if eligible) the Informed Consent process. In consultation with the site PI, treatment providers of patient participants will be recruited from each participating ED. When possible the study PI ([name]) or her designee will conduct an informational meeting about the study (conducted informally or during grand rounds or brown bag lunch sessions while onsite) for the purposes of orienting potential provider participants to the study and participation. Given the minimal risk nature of their engagement in this research and for efficiency, informed consent will be reviewed in this group format and questions will be addressed. Providers may opt to provide their consent at that time, or opt to complete the consent online at a later date (i.e., not during a group context). Providers may choose to contact the

research team at a later time to ask questions individually, learn more about the study, and/or provide consent at that later time. In all cases, researchers will connect via phone/email or in-person with the prospective provider participants and provide a high-level overview of the study.

Although potential participants may be informed of the study by their provider (in the case of patients) or their supervisor (in the case of providers), it will be made clear to all participants that the study is completely voluntary and will not affect their employment or treatment services. Partnering agencies and providers will be informed that there should be no coercion of potential participants to take part in the study.

## **B. Informed Consent**

Patients and providers who are interested in participating will complete a screen for eligibility. As part of the screening process, the potential participants will also answer demographic questions to assess whether our recruitment efforts are reaching a diverse group and to assess the characteristics of participants in the research. Eligible participants will then proceed to the Informed Consent procedure with a researcher, though participants may choose to review the consent form on their own if they prefer. All participants will be provided with an overview of the study and disclosure regarding what will be asked of them using Informed Consent procedures. The Informed Consent form will describe the study procedures and clarify that the study is completely voluntary and that participants may decline to participate at any time. For the ED study, the information provided to patients about Jaspr will be limited until after randomization to guard against disappointment or other negative feeling if assigned to the CAU condition. Once randomized, patients assigned to the Jaspr condition will be provided with the supplemental consent form with complete disclosure of the study procedures and information about Jaspr. These patient participants will have the chance to ask questions about Jaspr and the Jaspr study condition and decide if they want to continue their participation in the study. Once initial eligibility is determined, potential participants will be given a brief description of the study and asked for their verbal consent to proceed with the Informed Consent discussion. The Informed Consent process will take place in person with a member of the research team. The Informed Consent process will take place remotely via telephone and/or internet with a member of the research team.

All potential participants are informed during the Informed Consent procedure that participation is completely voluntary and that they may withdraw from the study at any time with no negative consequences. Eligible participants will receive a copy of the Informed Consent Form (via hard copy, or email). Participants will have the opportunity to read and review the consent form with the research staff, on their own, and/or review it with friends and family if desired. The researchers may use a high-level overview PowerPoint on their laptop computer to verbally and/or visually walk patients through the informed consent form and HIPAA Authorization (patients only). Study staff will be available to answer any questions or concerns the participants may have prior to signing and returning the consent form. For the ED study, patient participants assigned to the Jaspr condition will be walked through a supplement consent form with more information about the app, their signature will be collected for final consent, and they will receive an electronic or hard copy of the supplement consent form for their records.

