#### ED Study

**Patient Participants:** Because the patient's medical treatment is of foremost importance and to accommodate the fluid, unpredictable environments in the ED and to work within their usual flow, the researchers will pause all research procedures whenever necessary to allow for the patient's medical care and resume should there be additional periods of waiting. Once enrollment is complete (i.e., consent is obtained), the researchers will request a release of information from the participant for information we would like to gather from a member of their care team after the patient's discharge. Specifically, we are interested in collecting data about the patient's length of stay, if physical or chemical restraints were used and if so for how long, their final discharge disposition (e.g., if the patient was admitted to inpatient, residential, or substance abuse treatment or discharged to home), and if the patient was admitted whether it was involuntary or voluntary. This data will be obtained orally by speaking with a member of the patient's care team; medical records will not be accessed by the researchers. Permission (or not) for this release of information will not impact the patient's participation in the study (i.e., if they decline to provide permission for this release, they may still participate in the study). If the patient agrees to provide permission for the researcher to collect this information, they will be asked to sign a release of information form.

The researcher will then conduct the baseline assessment and the researcher will randomize the patient to condition while the participant is completing baseline measures. The researcher will inform the patient of the condition they have

been assigned after they have completed the baseline assessment.

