If the patient is assigned to the CAU condition, the researcher will conclude the session and tell the patient that they will return in two hours to complete the post treatment interview and online surveys. If the patient is assigned to the Jaspr condition, the researcher will walk the patient through a supplement consent form to provide further information about the app and obtain their electronic or paper/pencil signature. The researcher will orient the patient to the app on the study tablet, help them to set up their account, and let them know they may use Jaspr however they choose for up to two hours, not including breaks they may request or that may be needed in order to receive their standard medical care. The researcher will remain with the patient at all times while using Jaspr to answer any questions that the patient may have about Jaspr or the study; the researcher will not engage with the patient otherwise. After two hours of Jaspr use, the researcher will ask the patient to pause their use of Jaspr and conduct the post treatment interview and online surveys. If the patient indicates they are finished using Jaspr prior to the two hour timeframe, the researcher will conduct the post treatment interview and online surveys at that time. After the post treatment surveys are completed, researchers will orient the patient to installing the Jaspr-at-Home mobile app on their smartphone and ask them to use it however they see fit after being discharged. If the patient does not have access to their smartphone or if they prefer to install the app after they leave the ED, the researcher will provide email instructions for accessing and installing Jaspr-at-Home.

Patient participants will be asked to contact the researcher in the unlikely event that they are going to be discharged or transferred prior to completing the post treatment surveys so that the patient may complete the study procedures prior to leaving. Time spent completing the initial session (i.e., eligibility, consent, randomization, baseline, scheduling, and post assessment) is estimated to take approximately 2 – 4 hours depending on the number of breaks the patient is required or elects to take.

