Data will be entered online using an encrypted, secure online assessment tool such as SurveyMonkey. Missing values are coded as to reason missing (e.g., 'participant unable to be located,' 'participant refused to answer,' etc.). All data will be cleaned for logic and other types of errors using SPSS. With regards to dropouts and missing data, we plan to gather data for all participants at all time points, including from those who stop using Jaspr or JAH. This will allow us to conduct primary analyses on the intent-to-treat sample. To minimize missing data, we have included built-in incentives (i.e., bonus payments for completing all assessments) and training by [name] in methods to decrease attrition. To the extent that there is question about skipped or missed assessments, the software and analysis method we have chosen provides options for the handling of incomplete data. Preference will be given to those methods for which the assumptions (e.g., Missing at Random) are plausibly met and that have the least biased parameters.

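### ED study: a second consent given after randomisation to Jaspr patients only, with no rule for those who decline it, risks unequal loss from the two arms

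*Combined protocol and SAP*

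**What the plan says.** Section 5.A (ED Study) has the researcher randomise the patient during the baseline measures and then disclose the condition they have "been assigned after they have completed the baseline assessment". From there the arms part:

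- **Care as usual (CAU):** "If the patient is assigned to the CAU condition, the researcher will conclude the session" and returns two hours later for the post-treatment assessment.
- **Jaspr:** "the researcher will walk the patient through a supplement consent form to provide further information about the app" and obtains a signature, then moves on to orientation to the app. No branch is written for a patient who does not sign.

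Section 7.B describes the same step: "Once randomized, patients assigned to the Jaspr condition will be provided with the supplemental consent form". It says these patients can ask questions and "decide if they want to continue their participation in the study", and that "their signature will be collected for final consent". It also explains why disclosure is late: to spare patients allocated to CAU from disappointment. Separately, all participants are told that "they may withdraw from the study at any time with no negative consequences".

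On missing data, Section 5.B states: "we plan to gather data for all participants at all time points, including from those who stop using Jaspr or JAH". It says this will support primary analyses on the intent-to-treat sample, and it prefers missing-data methods whose assumptions, such as missing at random, are plausible. It names no specific method and no sensitivity analysis.

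**The concern.** The supplemental consent falls after allocation is known, occurs in one arm, and turns on the patient's reaction to the intervention. As worded, it asks whether to remain in the study, not just whether to use the app. A patient who says no has a baseline assessment and, on a plain reading, nothing afterwards.

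If decliners would have fared differently from those who sign, the Jaspr patients with follow-up data are no longer comparable with the CAU arm. The protocol does not say whether a decliner counts as randomised, is followed, is replaced, or stays in the intent-to-treat sample. Outcomes not collected at 7, 30 and 90 days cannot be fully recovered later.

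**Working it through.** **1. Does the follow-up commitment reach decliners?** Section 5.B specifically includes people who stop using the app. A decliner never started it, and Section 7.B frames the choice as study participation. In Section 5.A the hand-off to the blinded assessor, the scheduling of all three follow-ups and the Participant Information Form come after the post-treatment surveys. A patient who leaves at the supplemental consent has none of these in place. The general intention to collect data on everyone is therefore not backed by a procedure for this group.

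**2. The plan's own figures.** Section 5.B (Statistical Power Considerations) gives 24, then 72, then 90. For a within-between interaction with f = 0.25, two groups, m = 4 time points, correlation 0.5 and sphericity (the last three are assumptions), noncentrality = f² × N × m / (1 − 0.5). N = 24 gives power 0.816. Then 24 × 3.0 = 72 and 72 / 0.80 = 90. These reproduce and are not in dispute. The 20% attrition allowance is not split by arm or stage.

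**3. Size of a possible shift.** Inputs: 60 patients per arm (Section 3). Refusal share x and the difference D between decliners and signers in change from baseline are not given, so both are assumed. If decliners are lost and baseline does not explain the difference, the Jaspr mean change shifts by x × D. The type I error below is for a two-sided z test of 60 CAU against 60(1 − x) Jaspr patients, with SE = √(1/60 + 1/[60(1 − x)]). It takes one time point, unit SD and no design effect.

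| x | Decliners of 60 | Shift, D = 0.5 SD | Type I error | Shift, D = 1.0 SD | Type I error |
|---|---|---|---|---|---|
| 5% | 3 | 0.025 | 0.052 | 0.05 | 0.058 |
| 10% | 6 | 0.05 | 0.058 | 0.10 | 0.083 |
| 20% | 12 | 0.10 | 0.081 | 0.20 | 0.178 |

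With D = 0 the shift is 0 and the error stays at 0.05. The sign follows the sign of D.

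**4. Against the powered effect.** The plan applies f = 0.25 to the Time × Condition interaction. Suppose the arms differ by δ at all three follow-ups and by 0 at baseline. The mean difference over four time points is 0.75δ, so the interaction effects per cell are ±0.375δ once and ±0.125δ three times. Their SD is √[(0.1406 + 3 × 0.0156)/4] × δ = 0.2165δ. Setting this to 0.25 gives δ = 0.25 / 0.2165 = 1.15 SD. A shift of 0.025-0.10 SD is then 0.025/1.15 to 0.10/1.15, about 2-9% of that effect. With correlation 0.5, the SD of change equals the SD of the outcome, so the units agree.

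**5. Numbers analysed.** If refusals came on top of 20% attrition, the 90-patient minimum would leave 36 + 36(1 − x) = 70.2, 68.4 or 64.8 patients at x = 5, 10 or 20%, below the required 72. The target of 120 would leave 48 + 48(1 − x) = 93.6, 91.2 or 86.4, still above it.

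**The case against.** The other side has a good deal to say, and most of it limits the claim.

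- **Withdrawal rights are equal.** Patients in both arms may leave at any time. This stands: a reader might infer that only Jaspr patients can exit, but the asymmetry is an extra prompt and a required signature.
- **CAU patients may be lost too.** They also learn their allocation and are then left for two hours, while Jaspr patients have a researcher beside them. This stands: net loss, and the direction of any bias, cannot be read from the documents. A reader might infer that Jaspr is flattered, but decliners could equally be the less distressed patients.
- **The model keeps incomplete cases.** Baseline precedes disclosure, and the hierarchical model treats baseline as a time point. Baseline-only patients therefore enter the likelihood, and the estimate is valid if later data are missing at random given baseline and arm. A reader might infer that no mixed model can help; that goes too far. What remains is that refusal prompted by learning about Jaspr may well depend on unobserved outcomes, and nothing is planned to test this.
- **Some outcomes need no patient contact.** Disposition and restraint use come from the care team under a release requested before allocation. This stands in part: the protocol does not say whether declining would end that release.
- **Late disclosure has a stated purpose.** It does, and the purpose can be kept while the consequence of declining is changed.

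**Conclusion.** The point holds as a design risk confined to the ED study; no supplemental consent is described for the Telehealth study. A Jaspr-only exit point after randomisation exists on the face of the text, and decliners have neither a rule nor a route to follow-up.

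A reader might go further and conclude that the intent-to-treat comparison is biased. The documents do not support that. Bias needs refusals, decliners whose outcomes differ, and loss that is not at random. No refusal rate is given, and nowhere are decliners said to be excluded.

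Under the assumed 5-20% refusal and a 0.5 SD difference in change, the shift is about 0.025-0.10 SD in either direction, and zero if decliners do not differ. A reader might set this against a two-group medium effect of 0.5 SD and call it 5-20% of the target. The plan's f applies to the interaction, where under the constant-difference assumption the share is about 2-9%. The likely effect is modest, but it is avoidable at little cost.

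**What to change.** 1. Reword Section 7.B and the supplemental form so that declining the app is a separate choice from withdrawing from the study. Late disclosure and the right to withdraw stay as they are.
2. Add a branch to Section 5.A: a patient who declines Jaspr is asked to complete the post-treatment, 7-, 30- and 90-day assessments unless they separately withdraw. The blinded-assessor hand-off and follow-up scheduling take place at that point.
3. State in Section 5.B that all randomised patients are analysed in their assigned arm.
4. Report the number declining at this step, and withdrawals by arm.
5. Add a missing-not-at-random sensitivity analysis for those lost, for example shifting their imputed change by 0.25 to 1.0 SD in both directions.

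The cost is an IRB wording change, short additions to Sections 5.A and 5.B, and one extra analysis. Non-users remain in the Jaspr arm and dilute the effect slightly, which is what an intent-to-treat analysis accepts.
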